6.1 Information to be collected on screening failures

All patients who have signed informed consent but discontinue prior to first intake of study drug on Day 1 (Baseline Visit) are considered to be screen failures. If a patient discontinues prior to or at Day 1, the reason for screen failure will be entered on the Screening Phase Disposition eCRF.

The Screening Visit date, the Demography eCRF, the Informed Consent eCRF, the Inclusion/Exclusion eCRF, and the Patient Rescreening eCRF must be completed. The AE eCRF should be completed for any AEs that occurred during the Screening period. The withdrawal of consent eCRF must be completed if consent was withdrawn during the Screening period. The Death eCRF should be completed in the case of a death during the Screening period.

For all patients who sign the informed consent and enter into the next period of the study, all AEs occurring after the informed consent is signed will be recorded on the AE eCRF.

Investigators will have the discretion to record abnormal test findings on the medical history eCRF whenever in their judgment, the test abnormality occurred prior to the informed consent signature.

If a patient discontinues the study prior to entering the randomized, assessment-blinded treatment period (Treatment Period 2), the IRT should be notified and the reason for not being randomized (at Week 24) will be entered in the eCRF. The patient should be seen as soon as possible and treated as a discontinued patient as described in Section 5.5.10.

6.2 Patient demographics/other baseline characteristics

All Baseline assessments should be performed prior to first study drug administration. Please refer to Table 6-1.

6.2.1 Demographics

Patient demographic and Baseline characteristic data will be collected at the Screening Visit. Data to be collected on all patients include: date of birth (if allowed by local data privacy rules), age, sex, race, as well as height and weight.

6.2.2 Psoriasis medical history / previous psoriasis therapies

Disease history will be collected at the Screening Visit. The information to be collected and entered as Psoriasis History and Prior Psoriasis Therapies includes the following:

- The date of first diagnosis of chronic plaque psoriasis (by a physician).
- The previous treatments of psoriasis (including previous use of non-biologic systemic therapies, as well as phototherapy and/or photo chemotherapy) and the reason for discontinuation of each therapy.
- The presence of psoriatic arthritis and the date of first diagnosis (by a physician).

6.2.3 **Smoking history**

The current and/or previous use of tobacco products will be recorded, as well as the approximate consumption per year. Non-smokers will be advised not to start smoking during the study.

6.2.4 Co-morbidities – cardiovascular medical history

Any information pertaining to cardiovascular medical history assessed prior to signing of informed consent should be reported as cardiovascular history. Cardiovascular risk factors will also be recorded.

6.2.5 Relevant medical history / current medical conditions

Relevant medical history and current medical conditions, not including psoriasis or psoriatic arthritis, prior to signing of the informed consent will be recorded in the Medical History eCRF. Whenever possible, diagnoses and not symptoms will be recorded.

Patients with Crohn's Disease are eligible for the study, but should be followed closely.

Significant findings that are observed after the patient has signed the ICF and that meet the definition of an AE must be recorded in the AE summary pages.

6.2.5.1 Chest X-Ray

A chest X-ray, CT scan, or MRI obtained within 12 weeks prior to enrollment will be used to determine eligibility. If patients do not have a chest X-ray, CT scan, MRI available within 12 weeks prior to enrollment, a chest X-ray (or chest MRI at pre-specified sites) only must be done after it is fairly certain the patient meets the other inclusion/exclusion criteria in order to minimize unnecessary exposure to X-ray radiation for patients.

If the chest X-ray, CT scan, or MRI evaluated by a qualified physician shows evidence of ongoing infection or malignancy and the patient was not treated subsequent to the X-ray (CT scan or MRI), the patient will not be eligible to enter the study.

Prior and concomitant medications 6.2.6

Concomitant medications and prior medications taken over the 6 months preceding the study Screening Visit (Visit 1) will be captured in the eCRF and any other relevant medication taken before 6 months at the discretion of the Investigator.

6.2.7 **Determination of tuberculosis status**

Determination of TB status will be required before administration of study drug and should be performed as defined by local guidelines. TB status must be determined by medical history, signs, symptoms, and TB testing (QuantiFERON-TB Gold assay).

Any significant findings will be recorded in the TB Assessment eCRF and the Medical History eCRF, as necessary.

A QuantiFERON® TB-Gold In-Tube assay will be performed to assess the TB status at Screening for all patients. This test will only be used to determine patient's eligibility for the study. The test will be used to screen the patient population for latent TB infection (Doherty et al 2008). This blood-based assay is specific for *Mycobacterium tuberculosis* and is not influenced by previous Bacillus Calmette-Guérin vaccination or exposure to other Mycobacteria species. This test, in contrast to the purified protein derivative skin test, is also insensitive to a booster effect since the patient is not exposed to the vaccine. The assay measures the production of interferon-gamma and presents it relative to a negative and a positive control sample (Manuel and Kumar 2008). The QuantiFERON®-TB Gold assay test will be supplied by the central laboratory. Details on the collection, shipment of samples and reporting of results by the central laboratory are provided to Investigators in the laboratory manual.

- If the test result is negative, the patient may be enrolled.
- If the test result is positive, the Investigator should perform work-up for the test result as per local procedures. If a TB work-up was conducted prior to the Screening of the patient, results of the work-up can be used to assess eligibility if the work-up was conducted within 12 weeks prior to Baseline:
 - O Patients who are **positive** for latent TB per work-up may be enrolled in the study if sufficient treatment has been initiated according to local routine clinical practice and will be maintained for the prescribed duration. Patients **positive** for active TB per work-up are not eligible for the study.
 - o Patients who are **negative** for TB (no signs of latent or active TB) per work-up may be enrolled in the study.
- If the test result is **indeterminate**, it is **recommended to repeat the test once**. The Investigator may decide to skip the repetition of the test and proceed directly to the work-up (this is however not recommended). If a TB work-up was conducted prior to Screening the patient, results of the work-up can be used to assess eligibility if the work-up was conducted within 12 weeks prior to Day 1 (Baseline Visit).
 - o If the second test is **negative**, the patient may be enrolled.
 - o If the second test is **positive or** indeterminate, the Investigator should perform work-up as per local guidelines. The patient will not be eligible for enrollment if:
 - o "active TB is present" or
 - o "latent TB is present" and is untreated as per local guidelines. Patients negative for TB per work-up (no signs of latent or active TB) may be enrolled into the study if the work-up was conducted within 12 weeks prior to Day 1 (Baseline Visit).
- If eligibility is being assessed with only one test result and a TB work-up (ie, no second TB test will be performed), the TB test to assess eligibility must have been done via the central laboratory for the study within the Screening period (within 4 weeks prior to Day 1 [Baseline Visit]) and TB work-up will only be considered if it was completed within 12 weeks prior to Baseline. Patients who are positive for latent TB per work-up may be enrolled to the study if sufficient treatment has been initiated according to local routine

Amended Protocol Version v01 (Clean)

clinical practice and will be maintained for the prescribed duration. Patients positive for active TB per work-up are not eligible for the study. Patients negative for TB per work-up (no signs of latent or active TB) may be enrolled to the study.

QuantiFERON TB-Gold assay (QFT) Negative Indeterminate Positive QFT Subject REPEAT Eligible QFT ** Negative Indeterminate **Positive** QFT QFT QFT Subject Conduct TB Eligible workup per local guidelines Negative Positive workup Positive workup workup for LATENT for LATENTTB for ACTIVE TB or ACTIVE TB No TB Subject TB treatment Subject treatment Eligible initiated **NOT Eligible** initiated Subject

Figure 6-1 Tuberculosis screening flowchart

Abbreviations: TB: tuberculosis, QFT: QuantiFERON® TB-Gold In-Tube test

Eligible

The patient will not be eligible for enrollment if "active TB is present" or if "latent TB is present and is untreated as per local guidelines."

NOT Eligible

^{*} If the first QuantiFERON® TB-Gold In-Tube test is indeterminate, the Investigator may choose to perform a second test or refer the patient for TB work-up per local guidelines.

^{**} If the result of any QuantiFERON® TB-Gold In-Tube test is "positive" or the results of 2 sequential tests are "indeterminate," the patient must be referred to have a TB work-up per local guidelines (if no work-up within 12 weeks prior to enrollment is available).

6.2.8 Other baseline characteristics

Baseline characteristic data to be collected for all patients include (all laboratory tests are performed centrally except where indicated; see also Table 6-1) the following:

12-lead ECG, vital signs, hematology, clinical chemistry, physical examination, height, weight, past medical history record of HIV, Hepatitis B or C status, DLQI[©], WPAI-PSO, Patient's assessment of pain, itching and scaling, EQ-5D[©], as well as assessments of PASI, BSA and IGA mod 2011 and PK, if applicable. A serum pregnancy test will be performed for women of child-bearing potential.

6.3 Treatment exposure and compliance

All doses of study drug administered will be recorded on the appropriate Dosage Administration Record eCRF page. Patient compliance to the study drug should be assessed by qualified site personnel at each study visit using the study kits and documentation regarding study drug dispensation and administration.

Compliance will also be assessed continuously during the conduct of the study by Novartis study personnel using medication kits and corresponding documentation. Study drug doses and corresponding dates of self-administration at home should be documented in a selfadministration log. Patients are required to return the self-administration log as well as all dispensed study medication at every visit back to the investigational site for a compliance check.

6.4 **Efficacy**

All efficacy assessments should be performed prior to the administration of study drug.

Efficacy assessments

The efficacy assessments are recommended to be completed in the following order by the blinded PASI assessor. In all cases, the assessor will be blind to treatment allocation. Please refer to Section 5.4

- IGA mod 2011
- **PASI**

All remaining study visit procedures (eg laboratory sample collection, vital signs measurements, PK sample, if applicable) are recommended to be completed prior to administration of study drug.

Patient-reported outcomes

Patient reported outcomes are recommended to be performed in the following order, prior to any Investigator assessments:

- DLOI[©]
- Patient's assessment of pain, itching and scaling
- EO-5D[©]
- WPAI-PSO

Investigator's Global Assessment Modified 2011 6.4.1

The IGA mod 2011 will be conducted for overall psoriatic disease as indicated in the assessment schedule in Table 6-1. It is recommended that the same evaluator (ie, blinded assessor) conducts the assessment throughout the study wherever possible.

Patients require an IGA mod 2011 score at Baseline of 3 or 4 in order to participate in the study. Based on this scale, a patient will be considered as an IGA 0 or 1 responder if the patient achieves a score of 0 or 1, and improve by at least 2 points on the IGA scale at a given time point compared to their score at Baseline.

The IGA mod 2011 rating scale for overall psoriatic disease is shown in Table 6-3.

The IGA mod 2011 used in this study is static, ie, it refers exclusively to the patient's disease state at the time of the assessments, and does not attempt a comparison with any of the patient's previous disease states, whether at Baseline or at a previous visit.

The IGA mod 2011 score will be recorded in the eCRF.

Table 6-3 Investigator global assessment modified 2011 rating scale

Score	Short description	Detailed description
0	Clear	No signs of psoriasis. Post-inflammatory hyperpigmentation may be present
1	Almost clear	Normal to pink coloration of lesions; no thickening; no to minimal focal scaling
2	Mild	Pink to light red coloration; just detectable to mild thickening; predominantly fine scaling
3	Moderate	Dull bright red, clearly distinguishable erythema; clearly distinguishable to moderate thickening; moderate scaling
4	Severe	Bright to deep dark red coloration; severe thickening with hard edges; severe / coarse scaling covering almost all or all lesions

Note: Involvement of nails is not part of the assessment

6.4.2 Assessment of total body surface area and psoriasis area and severity

The blinded PASI assessor will complete the PASI assessment as indicated in Table 6-1. Whenever possible, the same blinded PASI assessor should perform this assessment at all visits.

The total BSA affected by plaque-type psoriasis will be estimated from the percentages of areas affected, including head, trunk, upper limbs and lower limbs (see below for full details of the PASI assessment). The following calculations will be done: Each reported percentage will be multiplied by its respective body region corresponding factor (head = 0.1, trunk = 0.3, upper limbs = 0.2, lower limbs = 0.4). The resulting 4 percentages will be added up to estimate the total BSA affected by chronic plaque psoriasis.

The PASI scoring system is further described in Table 6-4.

A PASI score (Fredriksson and Pettersson 1978; Weisman et al 2003; Gottlieb et al 2005) will be derived as indicated in Table 6-4. The head, trunk, upper limbs and lower limbs are assessed separately for erythema, thickening (plaque elevation, induration), and scaling (desquamation). The average degree of severity of each sign in each of the 4 body regions is assigned a score of 0-4. The area covered by lesions on each body region is estimated as a percentage of the total area of that particular body region. Further practical details to help with the assessment are provided below:

- 1. The neck is assessed as part of the head
- 2. The axillae and groin are assessed as part of the trunk
- 3. The buttocks are assessed as part of the lower limbs
- 4. When scoring the severity of erythema, scales should not be removed.

Because the head and neck, upper limbs, trunk and lower limbs correspond to approximately 10%, 20%, 30% and 40% of the BSA, respectively, the PASI score is calculated using the formula:

$$PASI = 0.1 (E_H + I_H + D_H)A_H + 0.2(E_U + I_U + D_U)A_U + 0.3(E_T + I_T + D_T)A_T + 0.4(E_L + I_L + D_L)A_L$$

The keys for the letters are provided in Table 6-4

PASI scores can range from a lower value of 0, corresponding to no signs of psoriasis, up to a theoretic maximum of 72.0.

The Baseline value for analysis of the PASI is collected at Day 1 (Baseline Visit).

Patients require a total BSA affected by plaque-type psoriasis of $\geq 10\%$ and a PASI score of \geq 10% at Baseline to be eligible for this study.

Table 6-4 Psoriasis area and severity index scoring system

Body region	Erythema (E)	Thickening (plaque elevation, induration, I)	Scaling (desquamation, D)	Area score (based on true area %, A)*
Head (H) [†]	0=none 1=slight 2=moderate 3=severe 4=very severe	0=none 1=slight 2=moderate 3=severe 4=very severe	0=none 1=slight 2=moderate 3=severe 4=very severe	0=no involvement 1=>0-<10% 2=10-<30% 3=30-<50% 4=50-<70% 5=70-<90% 6=90-100%
Trunk (T) [‡]	0=none 1=slight 2=moderate 3=severe 4=very severe	0=none 1=slight 2=moderate 3=severe 4=very severe	0=none 1=slight 2=moderate 3=severe 4=very severe	0=no involvement 1=>0-<10% 2=10-<30% 3=30-<50% 4=50-<70% 5=70-<90% 6=90-100%
Upper limbs (U)	0=none 1=slight 2=moderate 3=severe 4=very severe	0=none 1=slight 2=moderate 3=severe 4=very severe	0=none 1=slight 2=moderate 3=severe 4=very severe	0=no involvement 1=>0-<10% 2=10-<30% 3=30-<50% 4=50-<70% 5=70-<90% 6=90-100%
Lower limbs (L) [§]	0=none 1=slight 2=moderate 3=severe 4=very severe	0=none 1=slight 2=moderate 3=severe 4=very severe	0=none 1=slight 2=moderate 3=severe 4=very severe	0=no involvement 1=>0-<10% 2=10-<30% 3=30-<50% 4=50-<70% 5=70-<90% 6=90-100%

^{*}Percentage (not score) of body region (not whole body) affected will be entered in the eCRF

†Neck is assessed as part of the Head (H) body region

‡Axillae and groin are assessed as part of the Trunk (T) body region

[§]Buttocks are assessed as part of the Lower limbs (L) body region

6.4.3 Definitions of efficacy variables based on psoriasis area and severity index

The following definitions will be used in this study based on the Committee for Medicinal Products for Human Use (CHMP) guidelines for psoriasis (CHMP/EWP/2454/02 corr):

- PASI 50 response (partial response): patients achieving $\geq 50\%$ improvement (reduction) in PASI score compared to Baseline are defined as PASI 50 responders.
- PASI 75 response: patients achieving $\geq 75\%$ improvement (reduction) in PASI score compared to Baseline are defined as PASI 75 responders.
- PASI 90 response: patients achieving \geq 90% improvement (reduction) in PASI score compared to Baseline are defined as PASI 90 responders.
- **PASI 100 response / remission:** complete clearing of psoriasis (PASI = 0).

6.4.3.1 **Definitions of relapse and rebound**

For plaque psoriasis, in addition to the assessment of PASI, the Investigator will assess whether new pustular psoriasis, new erythrodermic psoriasis, or more inflammatory psoriasis has occurred (yes/no).

- **Relapse**: when the achieved maximal PASI improvement from Baseline is reduced by >50% (CHMP/EWP/2454/02 corr).
- **Rebound:** A patient will be considered to have experienced a rebound, if PASI increases to ≥125% of Baseline PASI, or if new pustular psoriasis, new erythrodermic psoriasis, or more inflammatory psoriasis occurs within 8 weeks after the last dose of study drug has been received (CHMP/EWP/2454/02 corr).

6.4.4 Appropriateness of efficacy assessments

PASI scores outcome measures, the assessment of the severity of the psoriasis symptoms and the extent to which the patient's body area is affected by the disease, is mandated by the EMA for the clinical investigation of medicinal products for the treatment of psoriasis (CHMP/EWP/2454/02 corr).

As indicated in Section 6.4.1, the IGA mod 2011 scale has been developed by Novartis (Langley et al 2013) in collaboration with health authorities, in particular the FDA and has been used extensively in the secukinumab in psoriasis Phase 3 program.

6.5 Safety

From Day 1 (Baseline Visit), all blood draws and safety assessments must be performed prior to study drug administration. Appropriate safety assessments (eg, evaluation of AEs and SAEs) should be repeated after the dose of study drug is administered.

- Evaluation of all AEs and SAEs including injection site hypersensitivity reactions, vital signs, laboratory assessments and occurrence of infections (see Section 7)
- Physical examination
- Vital signs
- Height and weight

- Laboratory evaluations (hematology, clinical chemistry including urine samples)
- 12-Lead ECGs
- Pregnancy and assessments of fertility

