The study drug will be self-administered by patients throughout the study. Study drug administration will occur at the study center for all study visits in Treatment Period 1; and at the study center or at the patient's home in Treatment Period 2. Self-administrations at every study center visit should be supervised by the study center personnel to ensure a correct study drug application and proper preparation of the patient for the home administration without study center personal supervision. If needed a caregiver of the patient can be trained for home administration to provide support. Home drug administration using the same injection device (ie, pre-filled syringes [PFS]) was introduced in previous secukinumab Phase 3b clinical studies, eg the CAIN457A2312, CAIN457A2313, and CAIN457A3301 studies. To allow for comparable treatment group data at fixed study visits, patients will be trained for home drug administration prior to Treatment Period 2.

A blinded PASI assessor who has no access to the randomization details must perform all PASI and IGA mod 2011 efficacy assessments for Treatment Period 2 (Week 24 to Week 52). To reduce measurement variability it is recommended that the same blinded PASI assessor performs all PASI and IGA mod 2011 assessments for a single patient.

The blinded PASI assessor must not participate in any study-related activities that could compromise the blinding and should solely concentrate on the skin examination for PASI and IGA mod 2011 assessments. For more details please refer to Section 5.4.

Safety will be assessed throughout the study through the monitoring of AEs, SAEs, electrocardiograms (ECGs), vital signs and laboratory data.

Figure 3-1 Study design

- **★** randomization of responder (PASI ≥ 90)
- randomization of responder (75 ≤ PASI < 90)
- BL: baseline
- NR: non-responder (PASI < 50)
- PE: primary endpoint
- PR: partial responder (50 ≤ PASI < 75)

Page 24

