5.5.4 Instructions for prescribing and taking study drug

Secukinumab will be self-administered by patients during the study after the study assessments (including completion of PROs) and scheduled blood samples have been performed.

For Treatment Period 1, all patients will be assigned to the same study drug regimen (300 mg secukinumab s.c. every week for the first 4 weeks, and thereafter every 4 weeks) and will self-administer the study drug at the study site under the supervision and guidance of site personnel at the time-points indicated in Table 5-1. To allow for comparable treatment group data on fixed study visits, patients will be trained for home drug administration prior to Treatment Period 2. If needed, a caregiver can be trained for home administration to provide support to the patient; corresponding training should be documented in the source data at the study center.

For Treatment Period 2, patients will be assigned to 4 different treatment interval groups depending on their PASI response at Week 24. Patients will self-administer their first dose of randomized study drug at Week 24 at the study site under the supervision and guidance of site personnel. Thereafter, patients will self-administer the study drug at either the study site or at home depending on the scheduled study drug administration by study group in Table 5-1 and Table 6-2.

Table 5-1 Timing of study drug administration by study group

_		
	Treatment Period 1	
	(Self-administration at Study Site)	(Self-administration at Home)
All Patients		
All patients	Baseline and	None
	Weeks 1, 2, 3, 4, 8, 12, 16 and 20	
	Treatment	Period 2
	(Self-administration at Study Site)	(Self-administration at Home)
Patients with PASI ≥ 90		
Group 1 (every 4 weeks)	Week 24, 28, 32, 36, 40, 44 and 48	None
Group 2 (every 6 weeks)	Week 24, 36, 48	Week 30, 42
Patients with 75 ≤ PASI < 90		
Group 3 (every 4 weeks)	Week 24, 28, 32, 36, 40, 44 and 48	None
Group 4 (every 2 weeks)	Week 24, 28, 32, 36, 40, 44 and 48	Week 26, 30, 34, 38, 42 and 46

Study drug will be dispensed and self-administered with the support of qualified personnel during office visits in accordance with local laws and regulations or self-administered at home. The blinded assessor for PASI and IGA mod 2011 must not be part of the study drug dispensing or administration process.

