7.1 Adverse events

An AE is any untoward medical occurrence (ie, any unfavorable and unintended sign [including abnormal laboratory findings], symptom or disease) in a patient or clinical investigation patient after providing written informed consent for participation in the study. Therefore, an AE may or may not be temporally or causally associated with the use of a medicinal (investigational) product. Study drug includes the investigational drug under evaluation and the comparator treatment that is given during any phase of the study. Medical conditions/diseases present before starting study drug are only considered AEs if they worsen after starting study drug.

All patients who have signed informed consent and are entered into the next period of the study will have all AEs occurring after informed consent is signed recorded on the AE eCRF.

The occurrence of AEs should be sought by non-directive questioning of the patient at each visit during the study. Adverse events also may be detected when they are volunteered by the patient during or between visits or through physical examination, laboratory test, or other assessments.

Abnormal laboratory values or test results constitute AEs only if they fulfill at least one of the following criteria:

- they induce clinical signs or symptoms.
- they are considered clinically significant.
- they require therapy.

Clinically significant abnormal laboratory values or test results should be identified through a review of values outside of normal ranges/clinically notable ranges, significant changes from Baseline or the previous visit, or values which are considered to be non-typical in patient with underlying disease. Investigators have the responsibility for managing the safety of individual patient and identifying AEs. Alert ranges for labs and other test abnormalities are included in Appendix 1.

Adverse events should be recorded in the AE eCRF with the following information:

- Severity grade:
 - o Mild: usually transient in nature and generally not interfering with normal activities.
 - o Moderate: sufficiently discomforting to interfere with normal activities.
 - Severe: prevents normal activities.
- Relationship of the AE to the study drug(s) (Suspected: Yes or No)
- Duration (start and end dates, or if the event is ongoing at the final examination).
- Whether it constitutes a SAE (see Section 7.2.1).
- Action taken with the study treatment.
- Concomitant medication or therapies taken.
- Outcome

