### 1.10 Compound specific safety evaluation

Safety topics of interest, such as risks defined in the Safety Profiling Plan, Risk Management Plan or topics of interest regarding signal detection or routine analysis are defined in the Program Case Retrieval Sheet that is stored in CREDI.

AEs of special interest (AESI) will be analyzed separately for Treatment Period 2 and the Entire Treatment Period. Crude incidence rates and corresponding confidence intervals of AESI will be summarized overall and by PT.

In addition, listings will be provided presenting which subjects experienced which risk.

The following AESI are part of the analysis.

- Major adverse cardiovascular events (MACE): identified per Novartis MedDRA Query (NMQ) "MACE (MI, Stroke, Cardiovascular death)"
- Inflammatory bowel disease: identified per NMQ "Inflammatory bowel disease"
- Candida infections: any AE with Candida high level term
- Malignancy: identified per NMQ "Malignant or unspecified tumours (excl. BCC and SCC)"
- Hypersensitivity and injection site reaction: identified per SMQ "Hypersensitivity"
- Hepatotoxicity: identified per SMQ "Drug related hepatic disorder severe events only"

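### In Treatment Period 2 only the 2-weekly and 6-weekly arms dose at home, with no described post-dose check, so by-regimen rates may understate immediate injection reactions in both

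*Protocol*

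**What the plan says.** **Where doses are given.** Protocol Table 5-1 (5.5.4) lists the Treatment Period 2 site doses of Groups 1 and 3 (4-weekly) as "Week 24, 28, 32, 36, 40, 44 and 48", with none at home. Group 4 (2-weekly) has the same seven site doses plus home doses at "Week 26, 30, 34, 38, 42 and 46". Group 2 (6-weekly) doses on site at Weeks 24, 36 and 48 and at home at Weeks 30 and 42. Table 6-2 agrees.

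**What happens around a dose.** Protocol 3.1: "Self-administrations at every study center visit should be supervised by the study center personnel". The same section describes training for "home administration without study center personal supervision". On safety assessments, Protocol 6.5 adds: "Appropriate safety assessments (eg, evaluation of AEs and SAEs) should be repeated after the dose of study drug is administered". It sets no observation time and describes no counterpart at home.

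**How reactions are otherwise found.** Protocol 7.1: "The occurrence of AEs should be sought by non-directive questioning of the patient at each visit during the study". Table 6-1 names injection-site reactions within the adverse event assessment, at the same visits for every group. For the home log, Protocol 6.3 says: "Study drug doses and corresponding dates of self-administration at home should be documented". No reaction field is described.

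**How they are analysed.** SAP 1.10 lists as an AESI "Hypersensitivity and injection site reaction: identified per SMQ" and summarises it by crude incidence with confidence intervals. SAP 1.9 presents Treatment Period 2 safety by three regimens: 2-weekly, 4-weekly (Groups 1 and 3 pooled) and 6-weekly. Neither document mentions the difference in place of dosing.

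**The concern.** A brief reaction soon after injection is most likely to be recorded if staff are present and ask about it after the dose. That opportunity exists for all 4-weekly doses, but only for part of the dosing in the two experimental regimens. The six doses that separate 2-weekly from 4-weekly dosing are all home doses, so the added exposure is the part with the weaker described ascertainment.

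If some brief reactions at home go unreported, both experimental regimens look better tolerated against 4-weekly dosing than they are. This deserves attention because Protocol 3.3 acknowledges that the 2-weekly regimen is untried as maintenance treatment, and Protocol 3.6 names hypersensitivity as a risk.

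**Working it through.** **1. Dose counts.** Inputs: Table 5-1. Weeks 24 to 48 span 24 weeks, so the schedules give 24/2 + 1 = 13, 24/4 + 1 = 7 and 24/6 + 1 = 5 doses, which matches the table. The documents state no home percentages; they follow from the counts.

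| Regimen | Site doses | Home doses | Home share |
|---|---|---|---|
| 2-weekly | 7 | 6 | 6/13 = 46.2% |
| 4-weekly | 7 | 0 | 0/7 = 0% |
| 6-weekly | 3 | 2 | 2/5 = 40.0% |

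**2. Time to the next questioning.** Visits fall at Weeks 28, 32, 36, 40, 44, 48 and 52 in all groups. Every home dose is nominally 2 weeks before the next visit (26 to 28, 30 to 32, and so on). Every site dose is 4 weeks before it.

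**3. Illustrative model.** Two quantities are assumptions and are not in the documents: q, the reaction risk per dose (doses independent), and r, the chance that a home reaction is recorded relative to a site reaction. With s site and h home doses:

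- share of reactions recorded = (s + r·h)/(s + h);
- observed patient incidence = 1 − (1 − q)^s × (1 − r·q)^h.

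The recorded share is (7 + 6r)/13 for 2-weekly and (3 + 2r)/5 for 6-weekly. At r = 0.5 these are 77% and 80%; at r = 0 they are 54% and 60%. At q = 1%:

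| r | 2-weekly | 4-weekly | 6-weekly | Ratio 2w/4w | Ratio 6w/4w |
|---|---|---|---|---|---|
| 1 | 12.25% | 6.79% | 4.90% | 1.80 | 0.72 |
| 0.75 | 10.91% | 6.79% | 4.42% | 1.61 | 0.65 |
| 0.5 | 9.55% | 6.79% | 3.94% | 1.41 | 0.58 |
| 0.25 | 8.18% | 6.79% | 3.45% | 1.20 | 0.51 |
| 0 | 6.79% | 6.79% | 2.97% | 1.00 | 0.44 |

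The choice of q matters little. From q = 0.2% to 2%, the 2w/4w ratio is 1.85 to 1.75 at r = 1 and 1.42 to 1.39 at r = 0.5. If r exceeds 1, as it might for later-onset reactions, the recorded share after home doses is the higher one and the 2w/4w ratio rises above its r = 1 value.

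**4. Scale in events.** Take the planned 105 patients in Group 4 (Protocol 9.7.1) and 570 in Group 2 (Protocol 9.7), full dosing, q = 1% and r = 0.5. Group 4 expects 105 × 13 × 0.01 = 13.65 reactions, of which 105 × (7 + 3) × 0.01 = 10.5 are recorded. Group 2 expects 570 × 5 × 0.01 = 28.5, of which 570 × (3 + 1) × 0.01 = 22.8 are recorded.

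**5. Restricting to common site doses.** Weeks 24, 36 and 48 are the only doses given on site in every group. Counting only these gives each regimen 1 − 0.99³ = 2.97%, a ratio of 1.00 for any pair. The difference in dosing frequency disappears.

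**The case against.** The case against making much of this is strong in several respects.

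- **Home reactions are not uncollected.** All groups share one visit calendar, injection-site reactions are named in the visit assessment, Protocol 7.1 lets patients report events themselves at or between visits, and unscheduled visits are available. Serious events have their own expedited reporting. The plausible loss is mainly brief, minor reactions. This stands.
- **The absence of a home check is inferred from silence.** Protocol 5.5.2 has patients record details that include the date, without saying that nothing else is recorded, and Protocol 5.5.3 leaves home handling to a separate document. The supervision and post-dose wording is also advisory. This stands, so the point can only be that no check is described.
- **The 2-weekly arm loses no checks.** It has seven site doses, as the 4-weekly arm does; the arm with fewer is the 6-weekly one, with three. True, but it does not remove the point, because the six additional 2-weekly doses are exactly those without a described check.
- **The direction is not certain.** A reaction that starts after the patient leaves the site is collected by recall in every arm, at 4 weeks after a site dose and 2 weeks after a home dose. Shorter recall could favour capture after home doses. This stands.

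A reader might infer that the plan probably flatters the intensified regimen or conceals harm. The documents do not support that: they give neither q nor r, any under-recording would affect the 6-weekly regimen to a similar degree, and the net direction depends on how many reactions are immediate.

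**Conclusion.** The difference in ascertainment is real and follows directly from the dosing tables: 0%, 46.2% and 40.0% of Treatment Period 2 doses are given at home under 4-, 2- and 6-weekly dosing, with no described post-dose check for those doses. It bears on immediate, short-lived reactions, whose crude by-regimen incidence may be understated in both experimental regimens.

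The size cannot be derived from the documents. It is zero if home reactions are reported as fully as site reactions (r = 1). The fall in the 2-weekly to 4-weekly ratio from 1.80 to 1.41 rests on an assumed q of 1% and r of 0.5, equal risk at every dose and independence between doses. For later-onset reactions the effect could reverse.

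Safety and tolerability is an exploratory objective (Protocol 2.3), and the AESI is summarised descriptively with no planned between-group test, so no confirmatory conclusion depends on it. This is a change to consider.

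**What to change.** 1. In SAP 1.10, keep the all-dose crude incidence by regimen as the main summary. It is the measure that carries the effect of dosing frequency.
2. Beside it, add events per 100 injections by dosing group, split by site and home doses, with the site versus home contrast within Group 4 and within Group 2 as a check on ascertainment. Take the place from the schedule and dosing records; dose dates and event start dates are already collected. Fix one onset window after each dose for all groups, since dosing intervals differ, and state whether the denominator counts doses or syringes, since each dose is two syringes.
3. A table restricted to Weeks 24, 36 and 48 may be shown as a supportive per-dose check. It should not be the basis of the between-regimen statement, for the reason in step 5 of the working.
4. For doses still to be given, record one identical yes/no reaction item for every Treatment Period 2 injection in all groups: on the self-administration log for home doses and in the dosing record for site doses. Asking it in every group avoids tilting the comparison the other way.

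The cost is one extra table and one line on existing records, with no added visits or patients. Some additional minor reactions may be reported. The within-group check will be imprecise: under the illustration, Group 4 would show about 105 × 7 × 0.01 = 7.35 site events against 105 × 6 × 0.005 = 3.15 home events. It can reveal a large gap but cannot exclude a modest one.
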